G* Power software 3.1 was used to calculate the required sample size, given a MANOVA test, an alpha of .05, power of 0.95, number of dependent variables of 4, number of groups of 2, and effect size of 0.25 (18). A sample size of 80 was calculated, and an attrition rate of 35% was added based on a previous study with variables similar to those of the present study (27). Therefore, this resulted in a final total sample size of 108 participants.

Instruments

The study data were collected using self-reported and physical measures. For the self-reported variables, a self-report questionnaire was used. The first part of the questionnaire included questions related to the behaviors and demographic characteristics of the participants, including age, religion, gender, marital status, daily consumption of cigarettes, general health status, nutritional status, coping behaviors, and sleeping hours and quality. Meanwhile, the second part included scales used to measure trait mindfulness and perceived stress. As for the physical variables, the enzyme-linked immunosorbent assay (ELISA) procedure was used to measure serum biomarkers such as serum cortisol and serum CRP.

Trait Mindfulness. Trait mindfulness was measured using the Arabic version of the Mindful Attention Awareness Scale (MAAS) (28), which is a one-dimensional scale that includes 15 items measured on a six-point Likert-type scale ranging from 1 (almost always) to 6 (almost never). The total possible score ranges between 15 and 90, with higher scores indicating higher levels of trait mindfulness. The original scale has been shown to have strong psychometric properties when validated among college students (28). Further, the Arabic version of this scale has been shown to have excellent internal consistency and convergent validity for use among Arab populations (29). In the current study, the Cronbach's alpha for the Arabic version of the MAAS was .79, indicating good internal consistency.

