The actual training sessions were introduced to the participants in the experimental groups by the PI based on Smith's (2005) guidelines and protocols. Based on the ABC Relaxation Theory (Smith, 1999, 2002, 2005), at least two, and preferably five, weekly sessions of actual mind-body training should be provided to evoke relaxation and optimize health (36, 37). The sessions were held in a private, quiet, comfortable, and spacious room at the university. As previously mentioned, the dependent variables were measured twice, at baseline and at the end of the intervention (i.e., In the next morning after the 5th session).

Various strategies were followed to decrease measurement errors that could potentially be affected by variations in the data collection procedure. For example, filling out the questionnaire may be stressful for some subjects, hence influencing the objective measures. Therefore, the self-report measures were completed after the physical measures were taken. Also, all of the study measures in the intervention and control groups were taken in similar conditions, including similar room temperature and environment. In addition, quiet environments were maintained, with a "Do Not Disturb" sign placed on the doors of the rooms during the interventions and data collection. The data (questionnaire and blood samples) were collected by three research assistants with at least 10 years nursing experiences who were not involved in any other parts of the study.

Statistical Analysis

Statistical analysis was conducted using SPSS software (version 25). First, the data were examined for outliers, missing data, and violations of statistical tests assumptions and managed as appropriate. Descriptive statistics were used to describe the sample. The sample and study variables were described by measures of central tendency and dispersion appropriate to the level of measurement. Initial independent t-tests and Chi-squared tests were conducted to ensure that the randomization across the covariates was successful, and one-way MANOVA was used to test the study hypotheses. Post hoc one-way ANOVAs were

run to examine if there were significant differences in each of the dependent variables between the study groups. Due to multiple testing, the p-value was adjusted by dividing the p value of .05 by 4 (i.e., the number of dependent variables), with a level of .0125 considered as the level of significance for the ANOVA tests.

References

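### Improvement, not an error: Holm's step-down could replace the fixed .0125 for the four post hoc ANOVAs and find more within the same .05 bound

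*Combined protocol and SAP*

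**What the plan says.** The Statistical Analysis section works in two steps. First, "one-way MANOVA was used to test the study hypotheses". Then come ANOVAs labelled post hoc, "run to examine if there were significant differences in each of the dependent variables between the study groups". To allow for the four tests in this second step, "the p-value was adjusted by dividing the p value of .05 by 4 (i.e., the number of dependent variables"). The section closes by setting one cut-off for all of them: "with a level of .0125 considered as the level of significance for the ANOVA tests". It is the same for all four outcomes (mindfulness, stress, cortisol and CRP). No ordered or step-down rule appears anywhere in the document.

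The words post hoc imply that the ANOVAs follow only a significant MANOVA, but the section does not state this outright.

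The Sample Size Calculation section sizes the trial on the first step only: "given a MANOVA test, an alpha of .05, power of 0.95, number of dependent variables of 4", with two groups and an effect size of 0.25, giving 80 before attrition. No power is given for any single outcome.

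**The concern.** The fixed .0125 is a valid rule, but it is stricter than its own .05 bound requires once one outcome has been declared significant. At that point at most three null hypotheses can still be true, yet the rule goes on paying for four.

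This matters because the Introduction states the aim as effects on four named outcomes, and the ANOVAs are the only planned step that answers outcome by outcome. The Introduction's causal model also expects the outcomes to move together: mindfulness rises, stress falls, and cortisol and CRP follow. A step-down rule helps most in that situation. At stake are outcomes that truly change but have p-values between .0125 and the threshold that Holm would allow.

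**Working it through.** **1. The plan's own figures.** .05 / 4 = .0125, as stated. The bound is 4 x .0125 = .05; for independent tests the error is 1 - (1 - .0125)^4 = .0491. The sample size also reproduces. For a two-group MANOVA with 4 outcomes, noncentrality is N x f2 = 80 x 0.25 = 20 on 4 and 75 degrees of freedom, and power at .05 is 0.952. The 0.95 is therefore power for the global test.

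**2. Holm's rule.** Order the four p-values and compare them with .05/4 = .0125, .05/3 = .0167, .05/2 = .025 and .05/1 = .05, stopping at the first failure.
- Every threshold is at least .0125, so anything Bonferroni rejects, Holm rejects.
- If m0 nulls are true, the first true null to be rejected meets a threshold of at most .05/m0. The chance that any of them passes it is at most m0 x .05/m0 = .05, whatever the correlations.
- A MANOVA gate can only remove rejections, so the bound holds with or without it.
- The first threshold is unchanged, so the chance of at least one rejection is identical.

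**3. Size of the gain.** Inputs from the documents: f2 = 0.25, N = 80, equal allocation, four outcomes. Assumed: multivariate normal data, the number of outcomes with equal effects, a common correlation, and the MANOVA as gate. For equal groups f2 = D^2/4, so D^2 = 4 x 0.25 = 1.0. With four equal effects d and common correlation r, D^2 = 4d^2/(1 + 3r), so d = 0.32, 0.50, 0.69 and 0.79 at r = -0.2, 0, 0.3 and 0.5. Part of the change across columns therefore comes from d.

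Average power per affected outcome, Bonferroni to Holm (simulation, 100,000 runs per setting):

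| Outcomes affected | r = -0.2 | r = 0 | r = 0.3 | r = 0.5 |
|---|---|---|---|---|
| Four | 0.133 to 0.140 | 0.378 to 0.446 | 0.697 to 0.796 | 0.825 to 0.893 |
| Three | 0.228 to 0.242 | 0.511 to 0.565 | 0.660 to 0.717 | 0.627 to 0.680 |
| Two | 0.462 to 0.482 | 0.723 to 0.750 | 0.731 to 0.755 | 0.626 to 0.649 |
| One | 0.909 to 0.909 | 0.945 to 0.946 | 0.916 to 0.917 | 0.826 to 0.827 |

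With the two questionnaires correlated 0.5 and all other pairs 0, four equal effects give 0.460 to 0.546; if only the questionnaires move, 0.891 to 0.904. No run had a Bonferroni rejection that Holm missed. Without the gate, the gains at r = 0 to 0.5 agree within 1 point.

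**4. Price.** Chance of a false claim on an unaffected outcome, Bonferroni against Holm, same gated setting:

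| Pattern | r = -0.2 | r = 0 | r = 0.3 | r = 0.5 |
|---|---|---|---|---|
| Three effects, one null | 0.013 v 0.017 | 0.012 v 0.026 | 0.013 v 0.035 | 0.012 v 0.032 |
| Two effects, two nulls | 0.025 v 0.035 | 0.026 v 0.043 | 0.025 v 0.040 | 0.024 v 0.037 |

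Shorter gated runs (40,000 per setting) give, for one effect and three nulls, 0.036 v 0.049, 0.035 v 0.045 and 0.033 v 0.041 at r = 0, 0.3 and 0.5. If only the two questionnaires move, the rate of false cortisol or CRP claims is about 0.025 v 0.046 to 0.048.

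Without the gate (200,000 runs, r = 0, 0.3 and 0.5), both rules give 0.050, 0.047 and 0.043 when nothing moves. With three very large effects and one null, Bonferroni gives 0.012 to 0.013 and Holm 0.050. That is Holm's limit, and it equals the plan's own bound.

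**The case against.** The plan names its family of four, sets its level and controls the error. Choosing between two valid rules is partly a matter of preference, and the better choice depends on which outcomes move. If only one moves, Holm adds false claims and no power. If only the questionnaires move, it buys about 1 point of power per outcome for about 2 points of false biomarker claims. The largest gains need all four outcomes to move equally with non-negative correlation, and only N = 80 has been examined although 108 were planned. The MANOVA, not the ANOVAs, is named as the test of the hypotheses.

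It may also be too late. The section is in the past tense ("Statistical analysis was conducted using SPSS software (version 25")) and the Instruments section already reports a reliability figure from this study ("alpha for the Arabic version of the MAAS was .79"). The reference list contains papers from 2021 although the protocol is dated July 2019. Relaxing a threshold after seeing data is what pre-specification is meant to prevent.

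Much of this stands: there is no error to correct, the gain depends on the pattern of effects, and timing limits the remedy. It does not remove the point. Every false-claim rate stays within the .05 that the plan itself chose as its limit, the Introduction expects the outcomes to move together, and the remedy differs according to whether data have been analysed.

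**Conclusion.** The point holds as an inexpensive improvement; the plan is not in error. That Holm rejects at least as much as Bonferroni under the same .05 bound needs no assumption about effects or correlations. The size of the benefit does. At correlations of 0 to 0.5 it is about 7 to 10, 5 to 6, 2 to 3 and 0 points of average power per affected outcome for four, three, two and one equal effects; at -0.2 it is 0 to 2 points. These figures assume normal data, 80 analysed, f2 = 0.25 and the MANOVA as gate. The MANOVA result and the chance of at least one significant outcome are unaffected. Holm uses more of the permitted .05 when some outcomes move and others do not.

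**What to change.** If outcome data have not been analysed, replace the fixed .0125 with Holm across the four ANOVA p-values: order them, compare with .0125, .0167, .025 and .05, and stop at the first that fails. Leave the MANOVA step as it is. This costs one sentence and no participants. Matching simultaneous confidence intervals are less simple under Holm, but the plan specifies none.

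If outcome data have been analysed, keep the .0125 results as primary and report Holm beside them, labelled as a change made later. The four p-values are all that is needed.

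At most, add to the Sample Size Calculation section that the 0.95 power refers to the global MANOVA and that no per-outcome power is given.
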